4.3 Rationale for choice of control drugs (comparator/placebo) or combination drugs

Currently there is no drug established as standard of care for participants with NASH. Combination of tropifexor and licogliflozin and each of these compounds as monotherapy will

Novartis	Confidential	Page 68 of 160
Amended Protocol Version 02 (Clean)		Protocol No. CLJN452D12201C

be compared to placebo. Subsequently, the combination treatment will be compared to each of the monotherapies.

A placebo treatment group was added to improve the assay sensitivity and interpretation of the treatment effect given the wide variability observed in histological response in recent studies for those participants receiving standard of care.

4.4 Purpose and timing of interim analyses/design adaptations

No interim analysis is planned for this study.

4.5 Risks and benefits

When used as monotherapy, tropifexor and licogliflozin have been shown to have potential benefits in treating NASH. Based on the mechanisms of action of FXR agonists and SGLT1/2 inhibitors and the fact that the biologic pathways do not overlap, it is expected that they will complement each other and address the three main pathologic features of NASH, namely steatosis, inflammation and fibrosis.

Appropriate eligibility criteria as well as specific stopping rules, are included in this protocol. Recommended guidelines for supportive management of study drug induced adverse events are provided in Section 10.2.

The risk to participants in this trial is minimized by compliance with the eligibility criteria and study procedures, as well as close clinical monitoring, stopping rules and periodic review of safety data by an independent DMC.

Toxicology of the combination is described in Section 1.1.9. All potential risks of each compound are described in the tropifexor and licogliflozin IBs. A brief summary of the benefits and risks of each compound follows:

4.5.1 Tropifexor

Based on the mechanism of action of tropifexor as a highly potent and specific agonist of the Farnesoid X Receptor (FXR) and data acquired in nonclinical toxicology studies, the First-in-Human study CLJN452X2101, and the ongoing Phase 2b CLJN452A2202 study, the risk-benefit assessment of tropifexor is as follows:

4.5.1.1 Benefits

Due to its multimodal mechanism of action, tropifexor treatment may have the anticipated benefits on biliary metabolism (reduced synthesis and increased detoxification), lipid distribution (lowering hepatic triglycerides accumulation) as well as anti-inflammatory and anti-fibrotic properties, leading to reduction of hepatic fibrosis and improvement of participant outcomes over longer term treatment. In study CLJN452A2202 in NASH, marked decreases in transaminases and in GGT, liver fat content and body weight were observed in a dose dependent manner, in participants receiving tropifexor compared to placebo.

4.5.1.2 Risks

Non-clinical

Liver effects: In rats, hepatic effects (hepatocellular vacuolation periportal hepatocellular hypertrophy, and bile duct hyperplasia as well as increases in FXR target gene for alkaline phosphatase expression) occurred at tropifexor doses ≥ 0.03 mg/kg/day in toxicity studies ranging from 2 weeks to 26 weeks in duration. All hepatic effects were either absent or decreased in incidence and severity by the end of the tropifexor-free recovery period indicating that full recovery would likely have been achieved with a longer recovery period. In addition, tropifexor was protective in various rodent models of liver disease/impairment including a model of drug-induced cholangiohepatitis and Alpha-naphthylisothiocyanate (ANIT) induced cholestasis.

Normal healthy human volunteers

Transient and asymptomatic increases in ALT were observed in healthy volunteers. This ALT increase was rapid in onset and resolved despite continued dosing, indicative of adaptation in humans.

NASH Participants

Of note, increases in transaminases similar to those observed in healthy volunteers were not seen in NASH participants in CLJN452A2202. Participants with impaired liver function and liver diseases other than NASH are excluded from the ELIVATE study (see exclusion criteria #9 and #10) and liver function tests including transaminases are monitored closely throughout study participation. Guidelines for the evaluation and detection of potential toxicities and for their management and for minimization of risk are discussed in the tropifexor IB and in Appendix 2 of this protocol.

Pruritus and lipid alterations (LDL-C elevation and HDL-C reduction) have been noted in clinical trials with FXR agonists (including tropifexor) and may be dose dependent. Both will be closely monitored in this study (please see the tropifexor IB for details).

Study CLJN452A2103 confirmed that the strong CYP3A4 inhibitor itraconazole increased the AUC of tropifexor by 47% and the strong CYP3A4 inducer rifampin decreased the AUC of tropifexor by 77-79% (Section 1.1.6.1). Therefore strong CYP3A4 inhibitors and inducers are prohibited during study participation (Section 6.2.2)

The Data Monitoring Committee (DMC) will review safety data at regular intervals throughout the study.

4.5.2 Licogliflozin

4.5.2.1 Benefits

Numerous lines of evidence, including data from a licogliflozin First-in-Human (FIH) clinical study CLIK066X2101, indicate that combining the effects of both SGLT1 and SGLT2 inhibition may offer more effective and safe treatment for obesity and diabetes via numerous mechanisms (Zambrowicz et al 2012). For example, SGLT2 inhibition increases urinary

Novartis	Confidential
Amended Protocol Version 02 (Clean)	

glucose excretion in both healthy participants and participants with T2DM, and lower glucose levels occur without hypoglycemia due to an insulin independent mechanism of action (Komoroski et al 2009a). Clinical validation of SGLT2 inhibitors as therapeutic targets for T2DM has been firmly demonstrated, and these compounds are now in wide use for T2DM (Wilding et al 2009, Komoroski et al 2009b). Agents such as dapagliflozin and canagliflozin also have additional beneficial effects on blood pressure and body weight (decrease ~2-3% compared to placebo; Scheen and Paquot 2014). In support of the link between obesity and hepatic injury related to excess accumulation of fat in the liver, weight loss leads to improvement in histologic NASH. This suggests that targeting obesity in NASH participants is likely a therapeutic opportunity to limit or reverse liver disease progression (Lassailly et al 2015, Vilar-Gomez et al 2015).

Inhibition of SGLT1 in the gut results in additional numerous weight-lowering mechanisms including calorie wasting from the gut, lower postprandial insulin levels, and an increase in incretin hormone (GLP-1, PYY) release as a consequence of distal, unabsorbed glucose in the gut (Sadry and Drucker 2013). When dosed close to a meal, licogliflozin has more marked efficacy in lowering postprandial glucose, lowering insulin levels, and increasing incretin hormones than when administered 6 hours or more prior to a meal, suggesting that gut luminal exposure to licogliflozin is required for SGLT1 inhibition. The additional benefit of SGLT1 inhibition also carries the risk of diarrhea due to glucose malabsorption. The orally administered, dual SGLT1/2 inhibitor licogliflozin has demonstrated safety, tolerability and efficacy in obesity and diabetes (LIK066 IB, Edition 10).

CLIK066X2204 study tested licogliflozin at doses of 30 and 150 mg for 12 weeks in NASH participants. Results from full study population confirmed that treatment with licogliflozin at 150 mg and 30 mg per day resulted in dose-dependent improvements in markers of liver injury (ALT, AST and GGT) and liver fat content(LIK066 IB edition 12). The clinical study report is currently in preparation. Both doses of licogliflozin led to significant placebo adjusted weight loss at the 150 mg and 30 mg doses respectively. (LIK066 IB). Licogliflozin treatment also improved glycemic and insulin sensitivity markers; HbA1c and HOMA-IR at both doses.

4.5.2.2 Risks

Risks of SGLT1/2 inhibition in human participants may include the development of diarrhea and genital and urinary tract infection (secondary to glucosuria). In study CLIK066X2204, the most common AE was diarrhea, reported by similar number of participants in the placebo and 30 mg groups but at a higher rate in the 150 mg dose group. As in previous studies with licogliflozin, diarrhea was mostly mild in the participants who had it. Only one participant in the 150 mg dose group discontinued treatment as a result of diarrhea (LIK066 IB Edition 12). Other potential risks based on reports with marketed SGLT2 inhibitors include hypoglycemia, Fournier's gangrene (necrotizing fasciitis of the genitalia and perineum), intravascular volume depletion, ketoacidosis, electrolyte disturbance and lower limb (toe) amputation. Appropriate exclusion criteria are applied in this study and guidance is provided to mitigate the risks as per Section 10.2.3. It is recommended that bilateral foot exams be performed at screening to assess the presence of any foot deformity (including amputation), disease, and/or the presence of clinically significant neuropathy that may increase the risk of amputation. Guidelines for the evaluation and detection of potential toxicities, their management and minimization of risk are discussed in detail in the LIK066 IB. The relatively low exposure associated with the dose of

Novartis	Confidential	Page 71 of 160
Amended Protocol Version 02 (Clean)		Protocol No. CLJN452D12201C

licogliflozin proposed in this study has been tested and is deemed safe in healthy participants, T2DM participants, and obese participants.

4.5.3 Study conduct

Women of child bearing potential must be informed that taking the study treatment may involve unknown risks to the fetus if pregnancy were to occur during the study and must agree that in order to participate in the study they must adhere to the contraception requirements outlined in the exclusion criteria. If there is any question that the participant will not reliably comply, they should not be entered or continue in the study.

Participants participating in this study might have reductions in hepatic fat and liver fibrosis; it is possible that this is a clinical benefit. For this reason, paired liver biopsies (Screening and Week 48) have been included in this study. Screening biopsies will confirm the diagnosis of NASH (steatosis, lobular inflammation, hepatocyte ballooning) and presence of fibrosis. The primary risks of liver biopsy are pain and bleeding from the site of needle entry into the liver, although the latter occurs in less than one percent of participants. Other possible major complications include the puncture of organs, such as the kidney, lung, colon, or the gallbladder. In order to reduce the risk of bleeding, the coagulation status must be assessed in all participants prior to a biopsy.

There may be participant benefit in the ancillary dietary and exercise counseling accompanying the pharmacologic intervention.

MRI makes use of powerful magnetic fields and radio waves, which are believed to cause no direct adverse consequences when used within approved specifications. No MRI-contrast will be administered in this study. Thus in principle, MRI scans can be repeated in the same participants as often as necessary. The MRI scanning equipment may cause a feeling of claustrophobia in susceptible persons; therefore, sensitivity to enclosed spaces should be queried at screening.

4.6 Rationale for Public Health Emergency mitigation procedures

During a public health emergency as declared by Local or Regional authorities, i.e., pandemic, epidemic or natural disaster, mitigation procedures to ensure participant safety and trial integrity are listed in relevant sections. Notification of the public health emergency should be discussed with Novartis prior to implementation of mitigation procedures, and should be permitted/approved by Local or Regional Health authorities and Ethics Committees as appropriate.

5 Study Population

The study population will consist of approximately 380 adult male and female participants with histologic evidence of NASH and fibrosis stage 2 or 3 as per NASH CRN histological score; see Inclusion and Exclusion criteria for details.

The study will be conducted in approximately 155 centers worldwide. Since a screening failure rate is expected to be around 70%, approximately 1267 participants may be screened.

The Investigator will ensure that all participants being considered for the study have met the eligibility criteria. No additional criteria should be applied by the investigator so that the study population will be representative of all eligible participants.

Participant selection will be established by checking through all inclusion/exclusion criteria at screening and Baseline. A relevant record of the eligibility criteria must be stored with the source documentation at the study center.

Deviation from any entry criterion excludes a participant from enrollment into the study.

5.1 Inclusion criteria

Participants eligible for inclusion in this study must meet **all** of the following criteria:

- 1. Signed informed consent must be obtained prior to participation in the study.
- 2. Male and female participants 18 years or older (at the time of the screening visit)
- 3. Presence of NASH with fibrosis confirmed by central reader's evaluation of liver biopsy obtained no more than 6 months before randomization as demonstrated by the following:
 - a. NASH using NAFLD Activity Score (NAS) ≥ 4 with at least 1 point each in inflammation and ballooning on the screening histology assessment performed by the central reader

and

- b. Fibrosis stage 2 or 3 using NASH CRN fibrosis criteria (see Table 8-2 & Table 8-3)
- 4. Able to communicate well with the investigator, to understand and comply with the requirements of the study

5.2 Exclusion criteria

Participants meeting any of the following criteria are not eligible for inclusion in this study.

- 1. Taking medications prohibited by the protocol. (see Section 6.2.2, Table 6-3)
- 2. Pregnant or nursing (lactating) women.
- 3. Weight at Baseline changed by > 5% since qualifying liver biopsy.
- 4. History of hypersensitivity to either of the study drugs or their excipients or to drugs of similar chemical classes, or participants with hereditary galactose intolerance, lactase deficiency or glucose-galactose malabsorption.
- 5. Taking a permitted medication listed in Table 6-2 but who is NOT on a stable dose (within 25% of Baseline dose) from the start of the screening period and
 - a. for at least 3 months prior to the Baseline visit for thyroid hormone, oral antidiabetic medication, insulin, GLP-1 agonists, and estrogen or estrogen containing birth control
 - b. for at least 6 months prior to Baseline for Vitamin E
- 6. Current, or history of, significant alcohol consumption for a period of more than 3 consecutive months within 1 year prior to screening.
 - a. Significant alcohol consumption is defined as more than 20 g/day (14 units/week) in females, or more than 30 g/day (21 units/week) in males, on

Novartis	Confidential	Page 73 of 160
Amended Protocol Version 02 (Clean)		Protocol No. CLJN452D12201C

average. A "unit" of alcohol is equivalent to one (12-ounce; 355 ml) beer, one glass (4-ounce; 120 ml) of wine, or 1 shot (ounce; 30 ml) of hard liquor.

or

- b. A score on the alcohol use disorders identification test (AUDIT) questionnaire ≥ 8 .
- 7. Diabetes related:
 - a. Type 1 diabetes mellitus.
 - b. Uncontrolled type 2 diabetes defined as $HbA1c \ge 9.0\%$ at screening.
 - c. HbA1c < 6.5% at screening in Type 2 diabetics currently treated with insulin or sulfonylureas.
- 8. Platelet count < LLN (see Central laboratory manual).
- 9. Clinical evidence of liver impairment as defined by the presence of any of the following abnormalities:
 - a. Serum albumin < LLN (see Central laboratory manual).
 - b. International Normalized Ratio (INR) > ULN (see Central laboratory manual).
 - c. ALT or $AST > 5 \times ULN$ (in either of the 2 values during screening).
 - d. Total bilirubin > ULN (see Central laboratory manual) (in either of the 2 values during screening), including Gilbert's syndrome.
 - e. Alkaline phosphatase > 300 IU/L (in either of the 2 values during screening).
 - f. History of esophageal varices, ascites or hepatic encephalopathy.
 - g. Splenomegaly.
 - h. MELD score >12.
- 10. Other forms of chronic liver disease:
 - a. Hepatitis B as defined by presence of hepatitis B surface antigen (HBsAg).
 - b. Hepatitis C as defined by presence of detectable hepatitis C virus (HCV) RNA.
 - c. Autoimmune liver disease.
 - d. Primary biliary cholangitis.
 - e. Primary sclerosing cholangitis
 - f. Wilson's disease.
 - g. Alpha-1-antitrypsin (A1AT) deficiency.
 - h. Hemochromatosis or iron overload.
 - i. Drug-induced liver disease as defined on the basis of typical exposure and history.
 - j. Bile duct obstruction.
 - k. Suspected or proven liver cancer.
 - 1. Any other type of liver disease other than NASH.
 - m. Hepatitis A as defined by presence of Immunoglobulin M (IgM) antibodies to HAV (IgM anti-HAV).
- 11. History of liver transplantation or planned liver transplant.
- 12. History of biliary diversion.

13. History or current diagnosis of ECG abnormalities based on Central ECG report indicating significant risk of safety for participants participating in the study such as:

- a. Concomitant clinically significant cardiac arrhythmias, e.g. sustained ventricular tachycardia, and clinically significant second or third degree AV block without a pacemaker.
- b. Resting QTcF \geq 450 msec (male) or \geq 460 msec (female) at pre-treatment screening.
- c. History of familial long OT syndrome or known family history of Torsade de Pointes.
- 14. Medical history of pancreatitis (acute or chronic).
- 15. Amylase and/or lipase >3 X ULN.
- 16. Prior or planned (during study period) bariatric surgery.
- 17. Calculated eGFR < 60 mL/min/1.73m2 (using the MDRD formula).
- 18. Hyperkalemia defined as potassium level > 5.2 millimoles per liter (mmol/L)
- 19. Chronic (> 3 months) use of excessive doses of Nonsteroidal Anti-inflammatory Drugs (NSAIDs) as evaluated by investigator.
- 20. Ketoacidosis, lactic acidosis, or hyperosmolar coma within six months of randomization.
- 21. History of lower limb amputation (including toe amputation) unless due to trauma.
- 22. Diabetic complications, known peripheral vascular disease or clinically significant neuropathy that may increase the risk of amputation.
- 23. Symptomatic genital or urinary tract infection within 4 weeks prior to randomization or participants with high risk as, determined by the investigator (including concomitant therapy with immunosuppressive potential), to be particularly susceptible to genital or urinary tract infection.
- 24. Recent history of gastrointestinal disorder associated with chronic diarrhea.
- 25. Any history of and/or suspected Fournier's gangrene, or participants with high risk as, determined by the investigator (including concomitant therapy with immunosuppressive potential), to be particularly susceptible to Fournier's gangrene.
- 26. Diabetic foot ulcer within 4 weeks prior to randomization.
- 27. History of inflammatory bowel disease (ulcerative colitis, Crohn's disease).
- 28. Known positivity for Human Immunodeficiency Virus (HIV) infection. HIV antigen/antibody tests will be performed to determine HIV status if allowed and required according to local regulations.
- 29. History of malignancy of any organ system (other than localized basal cell carcinoma of the skin or in situ cervical cancer), treated or untreated, within the past 5 years, regardless of whether there is evidence of local recurrence or metastases.
- 30. History or evidence of ongoing drug abuse, within the last 6 months prior to randomization.
- 31. Use of other investigational drugs within 5 half-lives of randomization, or within 30 days, whichever is longer.

- 32. Previous exposure to any other investigational or recently (2019 onwards) approved NASH treatment within 6 months prior to qualifying biopsy (participants known to have only received placebo may be included).
- 33. Sexually active males must use a condom during intercourse while taking drug and for 5 days after stopping investigational medication and should not father a child in this period. A condom is required to be used also by vasectomized men in order to prevent delivery of study drug via seminal fluid. (With-amendment version 01, this exclusion criterion is no longer applicable).
- 34. Women of child-bearing potential, defined as all women physiologically capable of becoming pregnant, unless they are using highly effective methods of contraception during dosing and for 5 days (> 5 times the terminal half-life) after stopping of investigational medication. Highly effective contraception methods include:
 - a. Total abstinence (when this is in line with the preferred and usual lifestyle of the participant). Periodic abstinence (e.g., calendar, ovulation, symptothermal, post-ovulation methods) and withdrawal are not acceptable methods of contraception.
 - b. Female sterilization (have had surgical bilateral oophorectomy with or without hysterectomy) total hysterectomy or bilateral tubal ligation at least six weeks before taking investigational drug. In case of oophorectomy alone, only when the reproductive status of the woman has been confirmed by follow up hormone level assessment.
 - c. Male sterilization (at least 6 months prior to screening). For female participants on the study, the vasectomized male partner should be the sole partner for that participant.
 - d. Use of oral, (estrogen and progesterone), injected or implanted hormonal methods of contraception or placement of an intrauterine device (IUD) or intrauterine system (IUS) or other forms of hormonal contraception that have comparable efficacy (failure rate <1%), for example hormone vaginal ring or transdermal hormone contraception.

In case of use of oral contraception women should have been stable on the same pill for a minimum of 3 months before taking investigational drug.

Women are considered post-menopausal if they have had 12 months of natural (spontaneous) amenorrhea with an appropriate clinical profile (e.g. age appropriate, history of vasomotor symptoms). Women are considered not of child bearing potential if they are post-menopausal or have had surgical bilateral oophorectomy (with or without hysterectomy), total hysterectomy or bilateral tubal ligation at least six weeks ago. In the case of oophorectomy alone, only when the reproductive status of the woman has been confirmed by follow up hormone level assessment is she considered not of child bearing potential. If local regulations deviate from the contraception methods listed above to prevent pregnancy, local regulations apply and will be described in the ICF.

35. Any other condition which, in the opinion of the investigator, would impede compliance or hinder completion of the study.

Novartis	Confidential	Page 76 of 160
Amended Protocol Version 02 (Clean)		Protocol No. CLJN452D12201C
Exclusionary laboratory tests can be rep	peated for eligib	ility during the screening period if the

Exclusionary laboratory tests can be repeated for eligibility during the screening period if the sample is compromised or otherwise reasonably suspected of being inaccurate.

6 Treatment

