GLP-1 agonists such as liraglutide, exenatide, lixisenatide, albiglutide or dulaglutide	At least 3 months prior to the Baseline visit
Beta-blockers and thiazide diuretics	At or before Screening Visit 1
Vitamin E < 800 IU/day	At least 6 months prior to the Baseline visit
Thyroid hormone	At least 3 months prior to the Baseline visit
Phenothiazines	At or before Screening Visit 1
Estrogen or estrogen containing birth control	At least 3 months prior to the Baseline visit

6.2.2 **Prohibited medication**

Use of the treatments displayed in the below Table 6-3 is NOT allowed after the start of investigational drug, and should be discontinued as soon as screening is considered so that participants medications and conditions are stable and the screening assessments reflect the participant's Baseline condition.

Alcohol consumption is to be strongly discouraged, and if consumed should not exceed 20 g/day (14 units/week) in females and 30 g/day (21 units/week) in males. A "unit" of alcohol is equivalent to 12-ounce, 355 ml beer, 4-ounce, 120 ml glass of wine, or 1 ounce, 30 ml shot of hard liquor.

Use of methotrexate is prohibited as liver fibrosis has been reported with its chronic use.

A study in healthy volunteers was conducted to investigate the effect of UDP glucuronosyltransferase (UGT) inhibition on the pharmacokinetics (PK) of tropifexor by coadministration with the UGT1A1 inhibitor, atazanavir (ATZ) (CLJN452A2110). The inhibition of UGT1A1 by ATZ did not lead to increased exposure of tropifexor, suggesting that inhibition of the UGT1A1 pathway has no clinically relevant impact on tropifexor PK. Therefore, no Drug-Drug Interactions are expected between tropifexor and UGT1A1 inhibitors based on UGT1A1 activity / genotype, and therefore use of these compounds is not prohibited in this study. Non-selective UGT inhibitors are prohibited.

Medication	Timing
SGLT2 Inhibitors or combined SGLT1/2 inhibitors	Stop at least 3 months prior to Baseline
Such as: canagliflozin, dapagliflozin, empagliflozin	
Pharmacologically active weight-loss medications	Stop at least 3 months prior to Baseline
Such as: lorcaserin, phentermine/topiramate, bupropion-naltrexone HCL, orlistat)	
Treatment with drugs that have a high incidence of diarrhea	Stop at or before Screening Visit 1
Such as: Orlistat, Acarbose.	
Treatment with drugs that alter intestinal motility	Stop at or before Screening Visit 1

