As per Section 4.6, during a public health emergency as declared by Local or Regional authorities, i.e; pandemic, epidemic or natural disaster that limits or prevents on-site study visits, alternative methods of providing continuing care may be implemented by the investigator as the situation dictates. If permitted by a Local Health authority and depending on operational capabilities, phone calls, virtual contacts (e.g., tele consult) or visits by site staff/ home nursing staff to the participant's home, can replace on-site study visits, for the duration of the disruption until it is safe for the participant to visit the site again.

Novartis	
Amended Protocol Version 02 (Clean)	

Confidential

Page **93** of **160** Protocol No. CLJN452D12201C

Table 8-1Assessment Schedule

Period	Scre	ening		Treatment											EOS/PSW
Visit Name	Screening 1	Screening 2	Baseline	W2	W4	W8	W12	W16	W20	W24	W32	W40	W48	Unscheduled	Follow-Up W52
Visit Number	1	2	3	4	5	6	7	8	9	10	11	12	13	-	14
Days	-70 to -42	-42 to -1	0	14	28	56	84	112	140	168	224	280	336	-	364
Weeks	-10 to -6	-6 to 0	0	2	4	8	12	16	20	24	32	40	48	0	52
Informed consent	Х														
Inclusion / Exclusion criteria	Х	х	х												
Demography	Х														
Medical history/current medical conditions	Х	Х	Х												
Protocol solicited medical history	х	х	х												
Randomization			Х												
Contact IRT	Х	Х	Х		Х	Х	Х	Х	Х	Х	Х	Х	Х	Х	Х
Physical Examination	S	S	S	S	s	S	S	s	S	S	S	S	S	S	S
Vital Signs ¹	Х	Х	х	Х	Х	Х	Х	Х	Х	Х	Х	Х	Х	Х	Х
Body Height	Х														
Body Weight	Х	Х	Х	Х	Х	Х	Х	Х	Х	Х	Х	Х	Х	Х	Х

Novartis			Confidential											Page 94 of 160			
Amended Protoco	I Version 02	2 (Clean)											Pro	otocol No. CLJ	452D12201C		
Period	Scre	ening				r	T	reatme	nt						EOS/PSW		
Visit Name	Screening 1	Screening 2	Baseline	W2	W4	W8	W12	W16	W20	W24	W32	W40	W48	Unscheduled	Follow-Up W52		
Visit Number	1	2	3	4	5	6	7	8	9	10	11	12	13	-	14		
Days	-70 to -42	-42 to -1	0	14	28	56	84	112	140	168	224	280	336	-	364		
Weeks	-10 to -6	-6 to 0	0	2	4	8	12	16	20	24	32	40	48	0	52		
Waist circumference	х	x	х				x			Х			х		Х		
Hip circumference	Х	Х	Х				х			Х			Х		Х		
Prior and ongoing / concomitant medications and non-drug therapies	х	x	х	х	x	х	x	x	х	х	x	х	x	х	х		
Alcohol history / compliance with protocol	х	х	х	х	х	х	x	x	х	Х	х	х	х	х	х		
Smoking history	Х																
Electrocardiogram (ECG) ²	х						x			Х			x				
Liver Biopsy ⁵		Х											Х				
Hepatitis serology ⁶	Х																

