8.2.4 Alcohol history and assessments

Any history of alcohol use will be recorded in the eCRF. At screening visit 2 the 10-item questionnaire Alcohol Use Disorders Identification Test (AUDIT) will be used. Further, for all the other visits the 3-item questionnaire, modified AUDIT will be administered to the participants as indicated in Table 8-1.

Optional: If the investigator requires additional data to evaluate the current alcohol use of the participant at the screening visit, the carbohydrate deficient transferrin (CDT) test can be assessed using the central lab.

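### The alcohol limits in 5.2 (6a) and 6.2.2 imply 10 g per unit, but the 355 ml beer listed as one unit holds 10 g only at about 3.6% strength, so counting beers as units can pass someone who is over the gram limit

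*Protocol*

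**What the plan says.** Criterion 6a in Protocol Section 5.2 excludes people with significant alcohol intake over more than three consecutive months in the year before screening. It gives the threshold as an average: "Significant alcohol consumption is defined as more than 20 g/day (14 units/week) in females, or more than 30 g/day (21 units/week) in males". It adds that one unit "of alcohol is equivalent to one (12-ounce; 355 ml) beer", a 120 ml glass of wine or a 30 ml shot of spirits.

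Section 6.2.2 (Prohibited medication) sets the on-study limit in the same two measures. Alcohol is discouraged and "if consumed should not exceed 20 g/day (14 units/week) in females and 30 g/day (21 units/week) in males". Its drink list repeats the same volumes, in the phrase "of alcohol is equivalent to 12-ounce, 355 ml beer, 4-ounce, 120 ml glass of wine, or 1 ounce, 30 ml shot of hard liquor".

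Neither section gives grams per unit or a drink strength, and neither says which measure governs if the two disagree.

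The limit is used in these places:
- Section 5 says "Deviation from any entry criterion excludes a participant from enrollment into the study".
- Table 8-1 has a row "Alcohol history / compliance with protocol", marked at every scheduled visit.
- Section 12.4 lists alcohol use above the permitted amount among the intercurrent events. Sections 2.1 and 12.4.3 then ignore it for estimation (treatment policy).

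Other alcohol controls are:
- an AUDIT score of 8 or more, which excludes separately under 6b;
- the questionnaires in Section 8.2.4: "At screening visit 2 the 10-item questionnaire Alcohol Use Disorders Identification Test (AUDIT) will be used", and "for all the other visits the 3-item questionnaire, modified AUDIT will be administered to the participants as indicated in Table 8-1";
- an optional carbohydrate-deficient transferrin (CDT) test at screening, also in Section 8.2.4.

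**The concern.** A limit stated in two measures works only if the conversion between them is right. Sites and participants count drinks more easily than grams. The Amendment 01 change log says units were added to criterion 6 because some participating countries commonly use them. If the listed drink holds more alcohol than the conversion assumes, the drink count is the looser rule. A person can then be within the unit limit and over the gram limit, and two of the roughly 155 planned centers could classify the same person differently. What is at stake is who enters under 6a and who is recorded as compliant on study, in a disease whose definition depends on excluding significant alcohol intake.

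**Working it through.** **Inputs.** The gram limits, unit limits and drink volumes come from Sections 5.2 and 6.2.2. Ethanol density is a physical constant, taken as 0.789 g/ml. Drink strengths are not in the documents and are assumed: beer 4–6%, wine 10–14%, spirits 40%.

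**1. The plan's own equivalence.** Grams per unit = (g/day × 7) ÷ (units/week).
- Women: 20 × 7 ÷ 14 = 10 g per unit.
- Men: 30 × 7 ÷ 21 = 10 g per unit.

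The two stated limits therefore agree with each other, at exactly 10 g per unit.

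**2. Strength at which each listed drink holds 10 g.** Strength = 10 ÷ (volume × 0.789).
- Beer, 355 ml: 10 ÷ (355 × 0.789) = 3.57%. Varying the density from 0.785 to 0.794 gives 3.59% to 3.55%.
- Wine, 120 ml: 10 ÷ (120 × 0.789) = 10.56%.
- Spirits, 30 ml: 10 ÷ (30 × 0.789) = 42.25%.

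Any beer above about 3.6% makes the unit count the looser rule. Below that strength the mismatch reverses: at 3% the beer holds 8.4 g.

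**3. Size for beer.** Grams per beer = 355 × strength × 0.789. The excess at the top of the unit range is grams per beer ÷ 10 − 1, the same for both sexes.

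| Assumed strength | g per beer | 14/week, g/day (limit 20) | 21/week, g/day (limit 30) | Excess |
|---|---|---|---|---|
| 4% | 11.2 | 22.4 | 33.6 | 12% |
| 5% | 14.0 | 28.0 | 42.0 | 40% |
| 6% | 16.8 | 33.6 | 50.4 | 68% |

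**4. Who falls between the two rules.** The gram limit is 140 g/week for women and 210 g/week for men. Dividing by grams per beer gives the weekly count that reaches it.

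| Assumed strength | Women: count at gram limit | Women: within units, over grams | Men: count at gram limit | Men: within units, over grams |
|---|---|---|---|---|
| 4% | 12.5 | 13–14 | 18.7 | 19–21 |
| 5% | 10.0 | 11–14 | 15.0 | 16–21 |
| 6% | 8.3 | 9–14 | 12.5 | 13–21 |

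At 5%, 10 and 15 beers sit on the limit. For example, a woman drinking 12 beers a week at 5% takes 12 × 14.0 ÷ 7 = 24 g/day. She passes on units and is excluded on grams.

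**5. Wine and spirits.**
- Wine, 120 ml, at 10, 12 and 14% holds 9.5, 11.4 and 13.3 g. At 10% no count conflicts. At 12% the conflicting counts are 13–14 glasses (women) and 19–21 (men); at 14% they are 11–14 and 16–21.
- Spirits, 30 ml, at 40% hold 9.5 g. That gives 18.9 g/day at 14 units and 28.4 g/day at 21, both under the limit.

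**The case against.** The strongest reply has four parts.

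**Grams already lead.** Criterion 6a defines the threshold in grams, with units in brackets. The change log presents units as an aid for countries that use them. The stated pairs agree exactly, and a conflict appears only once a beer strength is assumed. This stands as far as it goes: a careful reader would take grams as the definition. The drink list is still wrong for any beer above about 3.6%, and no sentence tells a site to set it aside.

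**Other controls overlap.** AUDIT, the modified AUDIT and the optional CDT test all bear on alcohol. Section 6.7.2.2 also asks participants to follow the American Heart Association diet or a local equivalent, and Appendix 5 of the protocol caps alcohol at one drink daily for women and two for men. If a drink there means one 355 ml beer (the appendix does not define it), adherence means at most 7 or 14 beers a week. Those counts lie below every conflicting band above, except 13–14 beers for men at 6%. This reduces the on-study effect. It is advice, a local diet may differ, and it does not bear on the pre-screening history that 6a judges. None of these controls settles whether grams or units apply.

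**Few people are affected.** The band holds people who drink mostly beer, close to the ceiling, with AUDIT below 8. For 6a, the intake must also have lasted more than three months. This stands, and the number cannot be derived from the documents.

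**A gram-based intercurrent-event flag cannot be assumed feasible.** The documents show an alcohol history and questionnaires, but not grams or drink strengths being captured. This stands, and no such flag is proposed.

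**Conclusion.** The inconsistency is real and minor. Both sections rest on 10 g per unit and then list a beer that holds 11.2–16.8 g at an assumed 4–6%. At the top of the unit range, a beer drinker is 12–68% over the gram limit. The direction holds for any beer above about 3.6%, whereas the size depends on the assumed strength. Wine shows a smaller gap and 40% spirits none.

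The effect is limited to eligibility under 6a and on-study alcohol compliance. Sample size, power and the primary test do not change.

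A reader might infer two stronger points that the documents do not support:
- **That the primary estimate is affected**, because alcohol overuse is a listed intercurrent event. Sections 2.1 and 12.4.3 give a specific rule for it: ignore it. Section 12.4.4 has a general sentence about imputing endpoints after intercurrent events, and the supplied SAP, which predates both amendments, also imputes after them. How that wording fits with 12.4.3 is a separate question and not evidence for this point.
- **That people enrolled on the unit count are entry deviations.** The Section 5 rule bars deviation from a criterion. It does not turn someone within the bracketed limit into a deviator.

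**What to change.** In Section 5.2 (6a) and Section 6.2.2, add one sentence: the limit in grams per day governs, and 1 unit is 10 g of alcohol. Then correct the drink list:
- **Beer:** either make one unit about 250 ml at 5% (250 × 0.05 × 0.789 = 9.9 g), or keep 355 ml and count it at 5% as 1.4 units (14.0 ÷ 10).
- **Wine:** keep 120 ml and state a strength of about 10.5% (120 × 0.105 × 0.789 = 9.9 g).
- **Spirits:** keep 30 ml and state a strength of about 40% (30 × 0.40 × 0.789 = 9.5 g).

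Apply this going forward, at the next amendment or through a clarification to sites. The cost is one sentence and a corrected list in each of two sections. The downside is that a few beer drinkers would be classified differently from people already enrolled on the unit count. No new derivation for the intercurrent-event flag is needed.
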